# 12.3.1Severity and Causality

The PI will grade the severity of each AE according to the Division of Aids Table for Grading the Severity of Adult and Pediatric Adverse Events Version 2.1, July, 2017, which can be found at

https://rsc.niaid.nih.gov/sites/default/files/daidsgradingcorrectedv21.pdf

**Causality** (likelihood that the event is related to the study agent) will be assessed considering the factors listed under the following categories:

# **Definitely related**

- Reasonable temporal relationship
- Follows a known response pattern
- Clear evidence to suggest a causal relationship
- There is no alternative etiology

# **Probably related**

Reasonable temporal relationship

- Follows a suspected response pattern (based on similar agents)
- No evidence of a more likely alternative etiology

## Possibly related

- Reasonable temporal relationship
- Little evidence for a more likely alternative etiology

# Unlikely related

- Does not have a reasonable temporal relationship OR
- Good evidence for a more likely alternative etiology

#### Not related

- Does not have a temporal relationship OR
- Definitely due to an alternative etiology

#### Note:

Other factors (e.g., dechallenge, rechallenge) should also be considered for each causality category when appropriate. Causality assessment is based on available information at the time of the assessment of the AE. The investigator may revise the causality assessment as additional information becomes available.

# 12.4 Investigator Reporting Responsibilities to the Sponsor

## 12.4.1 Adverse Events

Line listings, frequency tables, and other summary AE data will be submitted to the IND sponsor per the Safety Review and Communications Plan (SRCP – see below), or as needed for periodic safety assessments, review of IND annual reports, review of IND safety reports, and preparation of final study reports.

# 12.4.2 Serious Adverse Events (SAEs)

SAEs (whether or not they are also UPs) must be reported on the appropriate SAE/UP report form and sent to the sponsor Clinical Safety Office (CSO) by fax or email attachment. Deaths and immediately life-threatening SAEs must be reported within 1 business day after the site becomes aware of the event. All other SAEs must be reported within 3 business days of site awareness.

# 12.4.3 Unanticipated Problems (UPs)

Non-serious AEs that are UPs must also be reported on the NIH Problem report form and sent to the CSO by fax or e-mail attachment no later than 7 calendar days of site awareness of the event. UPs that are not AEs are not reported to the sponsor CSO.

# 12.4.4 Pregnancy

Pregnancy itself is not an AE. However, complications of pregnancies are AEs and may be SAEs. Pertinent obstetrical information for all pregnancies, including pregnancies disclosed by the subject as occurring in a partner of a male subject, will be reported to the CSO via fax or e-mail within 3 business days from the site awareness of the pregnancy.

Pregnancy outcome data (e.g., delivery outcome, spontaneous or elective termination of the pregnancy) will be reported to the CSO within 3 business days of the site awareness on a protocol-specified form. In the event of pregnancy, the following steps will be taken:

- Discontinuation of the study agents
- Unblind subject (Group 1 only)
- Withdraw from the study but continue following for safety
- Report to Medical Monitor and the IRB
- Advise research subject to notify the obstetrician of study agent exposure

## 12.5 Investigator Reporting Responsibilities to the NIH IRB

- Assessment of Safety: AEs and other reportable events are defined in Policy 801: Reporting Research Events
- Reporting to the NIAID Clinical Director: The principal investigator will report UPs, major protocol deviations, and deaths to the NIAID Clinical Director according to institutional timelines.
- Unanticipated problems, non-compliance, and other reportable events will be reported to the NIH IRB according to Policy 801.

# 12.6 Follow-up of Adverse Events and Serious Adverse Events

AEs that occur following enrollment of subjects (i.e., after the first dose of bNAb or placebo) are followed until the final outcome is known or until the end of the study follow-up period.

SAEs that that are assessed by the investigator to be possibly, probably, or definitely related to study agent/placebo and that have not resolved by the end of the follow-up period will be followed until the final outcome is known. If it is not possible to obtain a final outcome for an SAE (e.g. the subject is lost to follow up), the reason a final outcome could not be obtained will be recorded by the investigator on the AE Case Report form.

SAEs that occur after study completion that are reported to and are assessed by the investigator to be possibly, probably, or definitely related must be reported to the CSO, as described above.

# 12.7 Sponsor's Reporting Responsibilities

SUSARs as defined in 21 Code of Federal Regulations (CFR) 312.32 and determined by the IND sponsor will be reported to the FDA and all participating investigators as IND safety reports.

The IND sponsor will also submit an IND annual report of the progress of the investigation to the FDA as defined in 21 CFR 312.33.

# **12.8 Halting Criteria for the Protocol**

Halting the study requires immediate discontinuation of the study agents administered for all subjects and suspension of enrollment until a decision is made about whether or not to continue study agent administration.

The halting criteria (as determined by the study PI and IND sponsor secondary to aggregate data review) for this study include:

- Any SAE or grade 4 AE that is possibly, probably, definitely related to the study agent; OR
- Any safety issue that the study PI or IND sponsor determines should halt the study.

Any related AE that is ≥ grade 3 (not including transient, subjective infusion-related symptoms such as malaise, fatigue, headache, chills) will be reviewed within 48 hours of site awareness, by the PI and IND sponsor medical monitor, to consider the need for halting the protocol.

The PI and/or CSO will determine if the study should be halted. In addition, the FDA or DSMB may halt the study at any time following review of any safety concerns.

# 12.8.1 Reporting of Study Halting

If a halting rule is met, a description of the AE(s) or safety issue must be reported by the PI, within one business day, to the CSO and to the IRB by fax or email. The sponsor will notify the FDA as soon as possible that the study has been halted.

# 12.8.2 Resumption of a Halted Study

The IND Sponsor, in collaboration with the PI will determine if it is safe to resume the study. The PI will notify the IRB and DSMB of the decision on resumption of the study. The sponsor will notify the FDA as soon as possible that the study has been resumed after a halt.

## 12.9 Pausing Criteria for a Subject

The decision to suspend administration of the study agent for a single subject requires discontinuation of the study agent administrated for the study subject until a decision is made whether or not to continue study agent administration.

The pausing criteria for a single subject in this study include:

 A subject experiences an SAE or grade 3 or greater AE (not including transient, subjective infusion-related symptoms such as malaise, fatigue, headache, chills, or total bilirubin in subjects taking atazanavir) that is (as determined by the IND sponsor) possibly, probably, or definitely related to the study agent;

#### OR

 A subject experiences a grade 2 or higher ophthalmic AE, judged to be at least possibly related to 3BNC117 and/or 10-1074, or any grade 3 or 4 ophthalmic AE, regardless of causality assessment. Additional dosing for the subject will be halted pending review and recommendation by the study clinical safety officer.

#### OR

 Any safety issue that the PI determines should pause administration of the study agent to a single subject.

The CSO, in collaboration with the PI, may also pause for an individual subject or the entire group if a safety concern is identified during routine aggregate data analysis.

# 12.9.1 Reporting of Pause

If a pausing requirement is met, a description of the AE(s) or safety issue must be reported by the PI by fax or e-mail within 1 business day to the sponsor CSO, PI, IRB, and the Medical Monitor. The sponsor will notify the FDA as soon as possible that the study agent has been halted for an individual subject.

# 12.9.2 Resumption of Pausing for a Subject or Group

The CSO in collaboration with the PI will determine whether or not it is safe to resume administration of the study agent to the subject. The PI will notify the IRB of the decision to resume administration of the study agent prior to resumption. The sponsor will notify the FDA and DSMB as soon as possible that the study agent has been resumed for an individual subject.

A subject who does not resume study agent will continue to be followed for safety.

## 12.10 Withdrawal Criteria for an Individual Subject

An individual subject will be withdrawn for any of the following:

- An individual subject's decision. (The PI will attempt to determine the reason for the subject's decision and will strongly suggest a follow-up plan to help ensure the subject safely returns to baseline or better, if possible).
- Co-enrollment in a study with an investigational research agent (rare exception granted by the PI).
- Any SAE or grade 4 systemic infusion related symptom(s) or AE that is considered to be related to the study agent.
- Clinically significant type 1 hypersensitivity reaction associated with the study agent. In the event of a type 1 hypersensitivity reaction that is NOT considered to be clinically significant, (e.g., brief, mild, and self-limited skin reaction without other

- symptoms), the PI may consider possible additional infusions of the study agent with appropriate precautions.
- Any clinical AE, laboratory abnormality, or other medical condition or situation such that continued participation in the study would not be in the best interest of the subject. Subjects will be followed for the duration of the study for indicated safety assessments.
- Non-compliance with study procedures to the extent that it is potentially harmful to the subject or to the integrity of the study data.
- Pregnancy.
- Subject misses more than 2 study infusions.

If possible, all subjects who discontinue the study treatment prematurely will be followed for 6 months for all the study evaluations.

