## 5.3.1 Dose Adjustments and Modifications

Mild-moderate infusion related symptoms (Grade I-II), should they develop, will be managed by temporarily stopping the infusion until symptoms have resolved. For symptoms such as fever, myalgia, or urticaria, symptomatic treatment with standard doses of acetaminophen or antihistamines may be given. Once symptoms have resolved, the infusion will be restarted at half the initial rate. If symptoms recur following a reduced infusion rate and symptomatic treatment, the infusion will again be stopped until symptoms resolved and restarted at a lower rate. If the infusion cannot be completed within a 3-hour time frame because of recurrent symptoms, the infusion(s) will be discontinued for that visit.

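### For a related SAE or related grade 4 AE, Section 12.9.2 allows study agent to be resumed while Section 12.10 requires withdrawal, and nothing says which governs

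*Combined protocol and SAP*

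**What the plan says.** Three sections of the protocol decide whether a subject receives more study agent after a reaction.

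- **Section 5.3.1 (infusion management).** Its scope is set by grade: "Mild-moderate infusion related symptoms (Grade I-II), should they develop, will be managed by temporarily stopping the infusion until symptoms have resolved". It names urticaria among the symptoms: "For symptoms such as fever, myalgia, or urticaria, symptomatic treatment with standard doses of acetaminophen or antihistamines may be given". Then: "Once symptoms have resolved, the infusion will be restarted at half the initial rate".
- **Section 12.9 (pausing a subject).** The first trigger is "A subject experiences an SAE or grade 3 or greater AE (not including transient, subjective infusion-related symptoms such as malaise, fatigue, headache, chills", with a further exception for bilirubin in subjects on atazanavir. The event must be "possibly, probably, or definitely related to the study agent", and the IND sponsor makes that determination. Dosing stops pending a decision. Under Section 12.9.2 the sponsor's Clinical Safety Office (CSO), working with the PI, "will determine whether or not it is safe to resume administration of the study agent to the subject".
- **Section 12.10 (withdrawing a subject).** The list is mandatory. It includes "Any SAE or grade 4 systemic infusion related symptom(s) or AE that is considered to be related to the study agent", with no exception in that item. A separate item is "Clinically significant type 1 hypersensitivity reaction associated with the study agent"; here there is an exception, since after a reaction that is not clinically significant the PI may consider further infusions with precautions.

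Section 12.8 also makes an at least possibly related SAE or grade 4 AE a criterion for halting the whole study.

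**The concern.** A related SAE or related grade 4 AE meets both the pausing rule and the withdrawal rule. The first leads to a decision that may end in re-dosing; the second leaves no decision to make. A team that follows Sections 12.9 and 12.9.2 could properly resume dosing in a subject whom Section 12.10 says must be withdrawn.

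The main stake is patient safety, because these are the most serious related events in the trial. There is a secondary effect on the data. The primary objective is the safety of multiple doses, and this rule fixes how many further doses a subject receives after a serious related event. If the two readings are applied to different subjects, exposure after such events will not be comparable.

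**Working it through.** There is no figure to reproduce. The check sets trigger and consequence side by side, event by event.

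| Event | 5.3.1 | 12.9 and 12.9.2 | 12.10 | Result |
|---|---|---|---|---|
| Related SAE | Not addressed as such | Pause; resumption possible | Withdrawal | Conflict |
| Related grade 4 AE outside the 12.9 exceptions | Above its grade limit | Pause; resumption possible | Withdrawal | Conflict |
| Related grade 3 non-serious AE outside the exceptions | Above its grade limit | Pause; resumption possible | Below grade 4 | No conflict |
| Grade I-II infusion reaction also judged a clinically significant type 1 hypersensitivity reaction | Restart once resolved | General AE trigger not met | Withdrawal | Conflict, narrow |
| Other Grade I-II non-serious infusion symptom | Restart once resolved | General AE trigger not met | Not listed | No conflict |
| Grade 3 passing, subjective infusion symptom | Above its grade limit | Excepted | Below grade 4 | Gap, not a conflict |

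**Step 1: precedence.** The first two rows meet both rules in full. Section 12.9.2 excludes no event type from resumption. Section 12.10 does not refer back to Section 12.9, and Section 12.9 does not refer forward to Section 12.10.

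**Step 2: relatedness.** Section 12.3.1 defines five categories: definitely, probably, possibly, unlikely and not related. Sections 12.6, 12.8 and 12.9 count the first three. The primary endpoint in Section 3.2.1 counts only the first two. Section 12.10 uses none of them, so usage elsewhere does not settle its meaning. The consequences are:

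- Probably or definitely related SAE: Section 12.10 applies on either reading, so the conflict is certain.
- Possibly related SAE, if Section 12.10 means the first three categories: mandatory withdrawal, in conflict with Section 12.9.2.
- Possibly related SAE, if Section 12.10 means the first two: pause only, and dosing may resume.

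The same holds for a grade 4 AE.

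**Step 3: assessor.** Section 12.3 gives causality assessment to the PI, and Section 12.9 gives the pausing determination to the IND sponsor. Section 12.10 names nobody. If the two assessments differ, the text does not say which one triggers withdrawal.

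**Step 4: does the study halt settle it?** No. Section 12.8 stops dosing for everyone after such an event, and Section 12.8.2 governs resuming the study. Neither says whether the subject who had the event may be dosed again.

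**Step 5: urticaria.** Section 5.3.1 restarts a Grade I-II reaction after it resolves and does not refer to the hypersensitivity item in Section 12.10. If the reaction is not clinically significant, Section 12.10 leaves further infusions to the PI, which is compatible with a restart. The instructions oppose each other only when the same reaction is judged clinically significant.

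**The case against.** The best defence is that the sections form a sequence: Section 12.9 is a temporary hold and Section 12.10 lists final outcomes. On that reading Section 12.9.2 still has work to do, for grade 3 AEs, ophthalmic AEs and pauses at the PI's discretion. Nor could a site re-dose on its own authority. The CSO and PI decide together, the IRB is told before dosing resumes (Section 12.9.2), a DSMB recommendation is required when pausing or halting criteria are met (Section 12.13), and the event also meets a study halting criterion.

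This is a plausible reading, and the safeguards make a casual re-dosing unlikely. But the text does not state the sequence, and the safeguards say who decides rather than which rule binds them. The sequence also leaves the possibly related event unresolved, because it depends on what relatedness means in Section 12.10. The Safety Review and Communications Plan might address this, but the protocol describes it as an internal document and does not say that it does.

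Some stronger readings are tempting but unsupported:

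- **The same reaction is restarted, paused or withdrawn under three sections.** The grade limits mostly keep Section 5.3.1 apart from the other two. A related SAE would fall under Section 5.3.1 only if a Grade I-II reaction were also serious.
- **A grade 3 subjective infusion symptom has no stopping rule.** There is no grade-specific instruction, but the PI may pause for any safety issue (Section 12.9), and Section 12.10 allows withdrawal in the subject's interest. The exception appears in both 12.8 and 12.9 and looks deliberate.
- **The choice of rule changes who may be replaced.** Section 12.11 rules out replacement where the reason is a real or perceived effect of the agent, so these subjects are not replaceable on either reading.
- **Inconsistent handling would unbalance the arms.** The protocol gives no figure for this, and Group 1 subjects and site staff are blinded.

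**Conclusion.** The point holds as a contradiction in the protocol text. It covers two event classes directly (related SAE and related grade 4 AE), an undefined relatedness term that leaves the possibly related event open, and one narrow overlap for a Grade I-II reaction judged a clinically significant type 1 hypersensitivity reaction.

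The numerical effect on the analysis is nil at the planning stage: no sample size, power or confidence interval rests on this rule. AEs are recorded through follow-up whether or not dosing continues, so the direct effect is on exposure. The events should be rare. Section 1.1.3.4 reports no at least possibly related SAE among more than 160 recipients of either antibody or both. The number of planned infusion visits is therefore not a measure of size. The case for acting is that a single event is enough to raise the question, and it concerns re-exposure of a subject.

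Two assumptions about the Section 12.10 item are made: that grade 4 qualifies both the infusion symptoms and the AE, and that the relatedness clause also applies to the SAE. Looser readings would widen the conflict and are not relied on.

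**What to change.** The sponsor and investigator should:

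1. Reconcile Sections 12.9 and 12.9.2 with Section 12.10, stating which governs a related SAE and a related grade 4 AE, so that each has one outcome.
2. Express relatedness in Section 12.10 in the Section 12.3.1 categories, and name who makes the assessment and whose view prevails if the PI and sponsor differ.
3. Cross-refer Section 5.3.1 to the hypersensitivity item in Section 12.10, so that the restart instruction and the withdrawal rule cannot both apply to one reaction.

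A short table of event against outcome would make the result easy to check. The outcome for each event is for the sponsor and investigator to choose; this review does not propose one. The cost is an amendment to the wording, with no change to sample size, visits or analysis.

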# 12.11 Replacement for Withdrawn Subjects

Any subject who withdraws from the study, or who discontinues the study agent, prematurely, and whose reasons for withdrawing from the study or discontinuing study agent administration are unrelated to any real or perceived effect of the study agent or their administration, may be replaced at the discretion of the PI.

# 12.12 Safety Oversight

# 12.12.1 Safety Review and Communications Plan (SRCP)

A Safety Review and Communications Plan (SRCP) has been developed for the protocol. The SRCP is an internal communications document between the PI and the IND sponsor CSO, which delineates the safety oversight responsibilities of the PI, the CSO, and other stakeholders. The SRCP also includes the overall plan for conducting periodic safety surveillance assessments.

# 12.12.2 Sponsor Medical Monitor

A medical monitor, representing the IND sponsor (OCRPRO), has been appointed for the safety oversight in this clinical study. The sponsor medical monitor will be responsible for performing safety assessments as outlined in the SRCP.

## 12.13 Data Safety Monitoring Board (DSMB)

The NIAID Intramural DSMB includes independent experts that do not have direct involvement in the conduct of the study and have no significant conflicts of interests as defined by NIAID policy. The Board will review the study prior to initiation and twice a year thereafter. An alternative schedule may be indicated (i.e., interim analysis)]. The Board may convene additional reviews as necessary. The Board will review the study data to evaluate the safety, efficacy, study progress, and conduct of the study. All SAEs, all UPs, and all IND Safety Reports will be reported by the PI to the DSMB at the same time they are submitted to the IRB or IND Sponsor. The PI will notify the DSMB of any cases of intentional or unintentional unblinding as

soon as possible. The PI will notify the Board at the time pausing or halting criteria are met and obtain a recommendation concerning continuation, modification, or termination of the study. The PI will submit the written DSMB summary reports with recommendations to the IRB(s).

#### 13 CLINICAL MONITORING STRUCTURE

#### SITE MONITORING PLAN

As per ICH-GCP 5.18 and FDA 21 CFR 312.50, clinical protocols are required to be adequately monitored by the study sponsor. This study monitoring will be conducted according to the "NIAID Intramural Clinical Monitoring Guidelines." Monitors under contract to the NIAID/ OCRPRO will visit the clinical research site to monitor aspects of the study in accordance with the appropriate regulations and the approved protocol. The objectives of a monitoring visit will be: 1) to verify the existence of signed informed consent documents and documentation of the informed consent form (ICF) process for each monitored subject; 2) to verify the prompt and accurate recording of all monitored data points, and prompt reporting of all SAEs; 3) to compare CRIMSON data abstracts with individual subjects' records and source documents (subjects' charts, laboratory analyses and test results, physicians' progress notes, nurses' notes, and any other relevant original subject information); and 4) to help ensure investigators are in compliance with the protocol. The monitors also will inspect the clinical site regulatory files to ensure that regulatory requirements (Office for Human Research Protections [OHRP], FDA), and applicable guidelines (ICH-GCP) are being followed. During the monitoring visits, the investigator (and/or designee) and other study personnel will be available to discuss the study progress and monitoring visit.

The investigator (and/or designee) will make study documents (e.g., consent forms, CRIMSON data abstracts, and pertinent hospital or clinical records readily available for inspection by the local IRB, the FDA, the site monitors, and the NIAID staff for confirmation of the study data.

A specific protocol monitoring plan will be discussed with the PI and study staff prior to enrollment. The plan will outline the frequency of monitoring visits based on such factors as study enrollment, data collection status and regulatory obligations.

